While the efficacy and safety of intranasal corticosteroids (INCS), such as budesonide, are well-established for the long-term management of CRS, penetration of INCS into the paranasal sinuses is limited. A recent clinical trial led by [name] and colleagues at Washington University demonstrated that the addition of budesonide capsules to daily large-volume, low-pressure sinus saline irrigation for one month resulted in clinically meaningful improvement in self-reported functional status and quality of life measures as well as objective measurements of CRS. Like budesonide, mometasone furoate (MF) is a second-generation INC. Mometasone is currently used as an inhalational drug for the treatment of asthma, allergic rhinitis, and nasal polyps. Due to its increased lipophilicity and extensive hepatic metabolism, however, mometasone has a markedly reduced systemic availability as compared to budesonide. In a recent double-blinded, placebo-controlled randomized clinical trial (RCT), Harvey et al demonstrated that MF nasal irrigation was superior to MF nasal spray in the management of CRS symptoms following sinus surgery, as measured by patient-reported outcomes and endoscopic findings.

The goal of this research project is to explore the impact of the addition of mometasone to high-volume, low-pressure nasal sinus saline irrigation (aka "Neti-Pot"-type systems) for surgery-naïve patients with CRS without nasal polyps. The overall objective of this study is to optimize medical management of CRS symptoms prior to escalation of surgery, and to evaluate a clinically meaningful question of whether steroid nasal irrigation is superior to steroid spray with saline nasal irrigation alone.

The specific aims of this study are as follows:

1. Compare the effectiveness of MF nasal irrigation to that of MF nasal spray in the management of CRS symptoms in surgery-naïve patients.
2. Evaluate the effect of MF nasal saline irrigation on the HPA axis compared to that of MF nasal spray.

To answer the research questions, the study design will be a double-blinded, randomized clinical trial. Up to 50 adult patients with complaints of purulent nasal drainage accompanied by nasal obstruction, facial pain-pressure-fullness, or both and reduction or loss of smell for 12 weeks or greater will be eligible. The intervention will be 8 weeks of either 1) mometasone nasal saline irrigation *and* placebo nasal spray or 2) mometasone nasal spray *and* nasal saline irrigation. The primary outcome measure will be the average per-patient change in *SNOT-22* between the two treatment groups.

SYNOPSIS

Study Title	Effectiveness of Mometasone nasal irrigation for chronic rhinosinusitis.
Objective	The primary objective of this proposed project is to evaluate the effectiveness of MF nasal saline irrigation as compared to the commonly used MF nasal spray in the medical management of CRS symptoms in patients who have not undergone sinus surgery.
Study Period	Planned enrollment duration for each subject: 8 weeks Planned study duration: 1 year
Number of Patients	Up to 50 adult patients with complaints of purulent (not clear) nasal drainage accompanied by nasal obstruction, facial pain-pressure-fullness, or both and reduction or loss of smell for 12 weeks or greater.
Study Drug	Mometasone in the form of a nasal irrigation or nasal spray. Mometasone is an anti-inflammatory glucocorticoid steroid that is used for the treatment of asthma, allergic rhinitis, and nasal polyps
Study Design	Prospective randomized clinical trial
Inclusion and Exclusion Criteria	
Inclusion Criteria: Adults 18-70 years of age 12 weeks or longer of two or more of the following signs and symptom consistent with chronic rhinosinusitis (CRS)^{1, 2}: mucopurulent drainage (anterior, posterior, or both), nasal obstruction (congestion), facial pain-pressure-fullness, and decreased sense of smell AND inflammation documented by one or more of the following findings: purulent (not clear) mucus or edema in the middle meatus or ethmoid region, radiographic imaging showing inflammation of the paranasal sinuses
 
Exclusion criteria: Unable to speak English Polyps in nasal cavity or the middle meatus History of comorbid ciliary dyskinesia, cystic fibrosis or any other mucociliary condition Dependence on prolonged corticosteroid therapy for comorbid conditions, such as asthma and chronic obstructive pulmonary disease. History of oral or systematic antibiotic use in the past 2 weeks History of sinus surgery History of cerebrospinal fluid leak History of allergy to mometasone or other topical steroids Pregnant or breast feeding Current infection or history of one of the following infections: Tuberculosis (TB) lung infection, or Herpes infection of the eye. Baseline SNOT-22 total scores below 9 were excluded due to the inability to achieve a minimally clinically improved difference Known history of bleeding disorder, topical or injectable lidocaine allergy, use of blood thinners

Primary Outcome	The change in the SNOT-22 (©2006, Washington University, St. Louis, MO) score between baseline and eight-week intervention and calculated as: $\Delta\text{SNOT-22} = \text{SNOT-22}_{\text{baseline}} - \text{SNOT-22}_{\text{8-week follow-up}}$.
Measurements	SNOT-22; ACE-27 Comorbidity Index; Lund Kennedy Endoscopy Grading Scale Lund – MacKay CT score (not required); Global Clinical Impression Scale;

	Olfactory Dysfunction Outcomes Rating (ODOR)
Statistical Methodology	Within subject change in SNOT-22 between intervention groups.

I. Statement of the Research Problem

Definition and Burden of Rhinosinusitis

Chronic rhinosinusitis (CRS) is the inflammation of the paranasal sinuses and lining of the nasal cavity for 12 weeks or more and is characterized by symptoms of facial pain-pressure-fullness, nasal discharge, and nasal obstruction.¹ 1 in 8 adults are affected and over 30 million cases are diagnosed each year.^{2,3} Analysis of national ambulatory data demonstrates that rhinosinusitis accounts for more outpatient antibiotic prescriptions than any other diagnosis.⁴ Patients with CRS visit primary care clinicians twice as often as those without the disorder and have 5 times as many prescriptions filled.⁵ Approximately \$8.3 billion is spent annually on CRS, primarily on prescription drugs and office-based care.⁶ Surgery for CRS, which costs on average \$7,700 per patient, is performed nearly 250,000 times per year in the United States.⁷

CRS is primarily an inflammatory disease, with exacerbations often associated with concomitant infection. However, treating the episodic infections alone leaves the underlying condition untreated, likely contributing to an increased frequency of exacerbations. In this way, CRS is very similar to chronic bronchitis. CRS is associated with sinus edema and impaired mucociliary clearance. With edema-related obstruction and retained mucus, bacterial infection can more easily occur.¹

Medical Management

The medical management of CRS includes antibiotics, topical nasal steroid sprays, and saline irrigation. Antibiotics are often prescribed for CRS and national surveys suggest a large degree of over utilization with development of serious adverse side-effects and resistant organisms.⁸⁻²⁰

Nasal Sinus Irrigation

Nasal sinus saline irrigation (aka Neti-Pot) is widely recommended and is a common treatment for CRS. The use of either isotonic ("normal" saline) or hypertonic saline is recommended, and there have been over 12 studies examining the impact of saline irrigation in the management of CRS. A recent systematic review by Thomas et al.¹⁷ analyzed the best mechanism to distribute topical therapeutics to the sinuses in CRS patients. Large-volume, low-pressure irrigation devices resulted in better distribution to the nasal cavity and sinuses, especially after surgery, than low-volume devices. In addition, large-volume devices were found to overcome any adverse effects of head position or nasal cavity anatomy on sinus distribution. Due to its low cost, high patient acceptance, and high benefit-to-risk margin, large-volume, low-pressure saline sinus irrigation is a widely recommended treatment for CRS.^{7,11,14,15,17}

Topical Nasal Steroid Spray

Intranasal corticosteroid sprays (INCS) are established as safe and effective monotherapy or adjuvant treatments for CRS.^{21,22} A Cochrane Review in 2011²² examined the efficacy of topical steroids for CRS without polyps in five clinical trials. When compared to placebo, topical steroid improved symptom scores (standardised mean difference -0.37; 95% CI (-0.60 to -0.13), P = 0.002; five trials, n = 286) and had a greater proportion of responders (risk ratio 1.69; 95% CI (1.21 to 2.37), P = 0.002; four trials, n = 263). While the use of INCS is generally recommended in the setting of CRS, there is limited penetration of the steroid beyond the nasal cavity and into

the paranasal sinuses.^{23,24} Therefore, there has been great interest in the use of novel delivery approaches and devices to improve intra-sinus corticosteroid deposition.²⁵

Non-Standard Delivery of Topical Steroids

Three studies have examined the use of topical steroids delivered through low-pressure, high-volume saline irrigation. Snidvongs et al.²² examined a large cohort of patients with CRS (n=111), 49 of whom had a diagnosis of CRS without nasal polyps. Treatment was with once daily nasal irrigations of 1mg budesonide/betamethasone in 240 mL of normal saline in the immediate post-operative period. Significant improvements were seen in SNOT-20 scores (2.3 ± 1.1 vs 1.2 ± 0.9), symptom scores (2.5 ± 1.1 vs 1.4 ± 1.0) and Lund-Kennedy endoscopy scores (4.3 ± 2.0 vs 1.9 ± 1.6). No adverse outcomes were reported. An open-label prospective study (n=9) by [name] and colleagues at Washington University²⁶ evaluated the efficacy of once daily irrigation with budesonide (0.25 mg). Subjects also underwent adrenal function assessment with the cosyntropin test before and after budesonide therapy. All subjects showed appropriate adrenal response to cosyntropin stimulation before and after the budesonide trial, and the mean change in SNOT-20 scores before and after budesonide therapy was statistically and clinically significant. Steinke²⁷ conducted a prospective pilot study in 8 subjects with allergy, as defined by a positive skin prick test; 4 subjects were classified as having aspirin-exacerbated respiratory disease, and all but 1 had physician-diagnosed asthma. The subjects received a 3-month course of twice daily budesonide irrigations (500 µg into >100 ml saline). The median sinus CT score before treatment was 15 (maximum=30), which improved to 5 ($p < .05$) after treatment. After budesonide treatment, subjects' sinus scores decreased (mean \pm SD) from 43.1 ± 5.4 to 20.1 ± 3.0 ($P < .02$). In addition, subjects reported a significant improvement in sense of smell. Of the four patients with nasal polyps, three had complete resolution. The authors concluded that their study supports the concept that addition of budesonide inhalation suspension to standard nasal saline irrigation produces subjective and objective benefit in eosinophilic sinus disease. Furthermore, in a recently completed double-blinded, placebo-controlled, randomized clinical trial by [name] et al at Washington University (submitted), the addition of 1 mg of budesonide to daily large-volume, low-pressure sinus saline irrigation for one month resulted in clinically meaningful improvements in self-reported functional status and quality of life measures as well as objective measurements of chronic rhinosinusitis. Although the study included both patients with and without nasal polyps, patients with nasal polyps received only a minor benefit from budesonide. Patients with nasal polyps may have reduced topical application and penetration of budesonide as well as endotypes that are less responsive to the anti-inflammatory effects of glucocorticosteroids.

Like budesonide, mometasone furoate is a second-generation INC. The newest of the INCS, mometasone is currently used as an inhalational drug for the treatment of asthma, allergic rhinitis, and nasal polyps. Due to its increased lipophilicity and extensive hepatic metabolism, however, mometasone has a markedly reduced systemic availability as compared to budesonide (<0.1% versus 34%, respectively).²⁸ Furthermore, using various pharmacologic tests, including competition and McKenzie assays, mometasone has been shown to have higher potency than budesonide.²⁸ While corticosteroids can suppress the HPA axis, multiple studies have demonstrated that INCS have no significant impact on the HPA axis. In 6 randomized controlled parallel-group or placebo trials in adults and children, no evidence of HPA axis suppression was seen.²⁹

In a recent double-blinded, placebo-controlled randomized clinical trial (RCT), Harvey et al demonstrated that MF nasal irrigation was superior to MF nasal spray in the management of CRS symptoms following sinus surgery, as measured by patient-reported outcomes and

endoscopic findings.²³ In the study, participants were assigned to either mometasone capsules (2 mg daily) or placebo intervention for 12 months following sinus surgery. The MF nasal irrigation group had a significantly greater improvement in nasal blockage visual analog symptoms compared to that of the MF nasal spray group ($p=0.029$). Furthermore, on endoscopic examination, the MF nasal irrigation group had significantly greater disease suppression than the MF nasal spray group, as evidenced by lower modified Lund-Kennedy endoscopic scores ($p=0.018$). Harvey et al reported no adverse effects from their dosage of mometasone.

Due to mometasone's favorable pharmacologic properties, we propose to evaluate the effectiveness of the addition of mometasone to large-volume, low-pressure sinus saline irrigation for patients with CRS without polyps in a single-site randomized clinical trial. We hypothesize that the addition of MF to a large-volume, low-pressure sinus saline irrigation will result in clinically meaningful benefits for patients with CRS as measured by subjective and objective outcome measures. We anticipate that MF dispensed in a large volume, low-pressure device will be superior to that of MF nasal spray combined with nasal saline irrigation in the medical management of CRS in surgery-naïve, non-polyp patients.

II. Specific Aims

The primary objective of this proposed project is to evaluate the effectiveness of MF nasal saline irrigation as compared to the commonly used MF nasal spray in the medical management of CRS symptoms in patients who have not undergone sinus surgery.

Specifically, we propose:

1. Compare the effectiveness of MF nasal irrigation to that of MF nasal spray in the management of CRS symptoms in surgery-naïve, non-polyp patients.

Participants will be randomized to either 1) 8-weeks of MF nasal saline irrigation *and* placebo nasal spray or 2) MF nasal spray *and* nasal saline irrigation. The primary outcome measure will be the within subject changes in SNOT-22 scores pre-and post-treatment. We hypothesize that MF nasal saline irrigation, when compared to that of MF nasal spray alone, will be more effective in the treatment of CRS symptoms.

2. Evaluate the effect of MF nasal saline irrigation on the HPA axis compared to MF nasal spray 10 participants will be sampled from each study arm in order to ascertain the effect of mometasone nasal irrigation on the function of the hypothalamus-adrenal-pituitary (HPA) axis, as measured by the cosyntropin test before and after completion of intervention. In prior studies on the safety of MF nasal spray in children and adults, no discernible effects of MF nasal spray on the function of the HPA axis were reported.²⁹ To our knowledge, a study examining the impact of MF nasal saline irrigation on the HPA axis has not been performed. Based on prior studies demonstrating the safety of MF nasal spray, we hypothesize that MF nasal saline irrigation will have a negligible effect on the HPA axis. Furthermore, subjects will be queried throughout their participation in the study regarding any adverse events experienced with mometasone.

III. Experimental Plan, Methods, and Data Analysis

Study Design: Randomized clinical trial

Subjects: Up to 50 adult patients with complaints of purulent nasal drainage accompanied by nasal obstruction, facial pain-pressure-fullness, or both and reduction or loss of smell for 12 weeks or greater.

Inclusion Criteria:

Adults 18-70 years of age

Twelve (12) weeks or longer of two or more of the following signs and symptom consistent with chronic rhinosinusitis (CRS)^{30,31}.

mucopurulent drainage (anterior, posterior, or both), nasal obstruction (congestion), facial pain-pressure-fullness, and decreased sense of smell

AND inflammation documented by one or more of the following findings:

2.5% of the dose remains in the nasal cavity following irrigation

2.4 mg x 0.025= 0.06 mg or 60 mcg

Harvey et al recently completed a study evaluated the effectiveness of mometasone nasal irrigation dosed at 2 mg daily for management of CRS symptoms following sinus surgery with no adverse effects reported during the study's yearlong duration.³⁰

Participants will be provided with a 2-month supply of either 1) MF nasal spray *and* nasal saline irrigation *or* 2) MF nasal irrigation *and* placebo nasal spray.

All participants will be provided with an 8-ounce (240 ml) NeilMed Sinus Rinse Regular Bottle Kit and a two-month supply of USP Grade Sodium Chloride & Sodium Bicarbonate Mixture (pH balanced, Isotonic & Preservative & Iodine Free) commercially prepared packets. Subjects may substitute the NeilMed Sinus Rinse Regular Bottle Kit for a nasal irrigation system, which in the opinion of the Principal Investigator, is similar to the NeilMed system and embodies the low-pressure, high-volume concept of nasal irrigation. Examples of such systems include, but are not limited to, ceramic or plastic neti pot or nasal douch (Nasendusche). Subjects will need to purchase distilled water or boil tap water for five minutes for use with the saline irrigation. Subjects will be required to dissolve the contents of two capsules (either mometasone or lactose placebo) into the 8-ounce (240 ml) NeilMed Sinus Rinse Regular Bottle along with the saline rinse. All subjects will be instructed to irrigate both right and left nasal cavity with one-half of the contents of the nasal rinse once daily. The subjects will receive written instructions and a video prior to initiation of the intervention to ensure proper delivery.

For participants randomized to MF nasal spray, they will be instructed to perform the following once daily: nasal saline irrigation with lactose placebo capsules as outlined above immediately followed by 2 sprays per nostril of MF nasal spray. For participants receiving MF nasal irrigation, they will be instructed to perform the following once daily: nasal saline irrigation with mometasone capsules as outlined above immediately followed by 2 sprays per nostril of the placebo spray.

Subjects randomized to the mometasone nasal irrigation intervention arm will be required to mix 2.4 mg of mometasone into the sinus rinse bottle and rinse each nasal cavity with one half of the bottle (~ 4 ounces or ~120 ml) daily. The inert ingredients are: loxasperse powder, which increases solubility and dispersibility of mometasone and is microbiologically safe; mannitol, which is widely used in pharmaceutical products as a capsule diluent; and Xylifos™ powder, which is a proprietary powder excipient used safely in pharmaceutical compounding for nasal nebulization or nasal irrigation.

Placebo Nasal Spray

The placebo nasal spray will be packaged in the same bottle as that of MF nasal spray. The nasal spray will be prepared by Advanced Rx Pharmacy and will contain the same inert ingredients found in MF nasal spray: glycerin, microcystalline cellulose and carboxymethylcellulose sodium, sodium citrate, citric acid, benzalkonium chloride, and polysorbate 80. Subjects in the mometasone nasal irrigation arm will be instructed to first irrigate with mometasone followed by use of the placebo nasal spray.

Mometasone Nasal Spray

Subjects randomized to the mometasone spray intervention arm will receive a 2 month supply of MF nasal spray (50 mcg/spray), which is commercially available as Nasonex™, but will be prepared for the study by Advanced Rx Pharmacy. Participants will be instructed to use 2 sprays per nostril once a day followed by nasal saline irrigation

Placebo Nasal Irrigation

The placebo product will contain lactose monohydrate and will be supplied in clear plastic capsules, which are identical to the budesonide capsules. The capsules will only contain lactose as there are no other ingredients.

Cosyntropin Test

Measuring blood levels of cortisol after cosyntropin stimulation is the gold standard to evaluate effects of exogenous corticosteroids on the HPA axis. The effects of mometasone nasal spray on the hypothalamus-pituitary-adrenal (HPA) axis have been evaluated in 6 clinical trials in both adults and children (dose range 100 ug once daily to 400 ug twice daily). In all 6 trials, no effects of mometasone nasal spray on the HPA axis was discernible.²⁹ To our knowledge, a similar demonstration of the safety of a nasally administered mometasone wash has not been performed. As a result, ten participants from each study arm will be selected for an optional cosyntropin test to assess the effect of mometasone nasal irrigation on the HPA axis.

Baseline levels of serum cortisol will be measured at the subject's first visit. Subjects will then receive 0.25 mg of cosyntropin and 10 mg of mannitol reconstituted with 1 mL of 0.9% sodium chloride as an intramuscular injection to stimulate the adrenal cortex. Serum will be drawn 30 minutes and cortisol level measured. This test will be repeated upon the completion of 60 days of mometasone nasal irrigation or spray. If mometasone is absorbed systemically via nasal irrigation, serum cortisol should be inappropriately low upon cosyntropin stimulation compared to baseline. No change in serum cortisol is expected in the mometasone nasal spray group based on prior studies. The cosyntropin test will be performed at the Center for Outpatient Health and blood cortisol levels measured by the General Clinical Research Center Immunoassay Core Laboratory.

In the event that at the first pre-intervention cosyntropin visit, a post-stimulation level is below the critical level of 18 µg/dL, indicating an insufficient adrenal response, the PI will be notified and the study participant contacted. With an abnormal cortisol level pre-intervention, the study participant will not be eligible for further participation in the study and the study coordinator will recommend that the participant be evaluated by his/her primary care physician.

In the event that a post-stimulation level is below the critical level of 18 µg/dL indicating an insufficient adrenal response, the PI will be notified and the study coordinator will notify the patient and recommend a referral to the study participant's primary care physician. Study participants in either intervention arm will remain on the intervention until cosyntropin lab values are received and reviewed.

Because certain medical conditions and medications can affect the cosyntropin test and result in spurious results, subjects will also be excluded from the test if they met any one of the following criteria: concurrent or recent use (within the past 30 days) of systemic corticosteroids; history of pituitary disease; morbid obesity as measured by body mass index; concurrent or recent use of medications that accelerate the clearance of cortisol, such as dilantin, rifampin, amphetamines, or lithium carbonate; concurrent use of medications that interfere with the production of cortisol, such as ketoconazole, amphotericin B, bupropion, Echinacea, fluoroquinolones, itraconazole, licorice, and ma huang (Ephedra); use of oral contraception; use of female or male hormone therapy; a radioactive scan performed within 7 days before the test; known hypersensitivity to cortisol, corticotropin, or cosyntropin; allergic disease associated with anaphylactic reactions or breathing difficulties; or pregnancy.

Exemption From IND Requirements

The use of mometasone in a nasal saline rinse is a change in the approved route of administration. An exemption from IND requirements will be requested as the proposed use of mometasone in this study fulfills all of the criteria for exemption:

1. Mometasone is lawfully marketed in the United States.
2. This study is not intended to be reported to the FDA in support of a new indication or significant change in labeling.
3. This study is not intended to support a significant change in the advertising for the drug.
4. The study does not involve a route of administration, dose, patient population, or other factor that significantly increases the risk (or decreases the acceptability of the risk) associated with the use of mometasone.
5. The study will be conducted in compliance with the requirements for review by an IRB (21 CFR part 56) and with the requirements for informed consent (21 CFR part 50).
6. The study is not intended to promote or commercialize mometasone.

Concomitant Medications

At the time of enrollment, subjects may already be using a topical nasal steroid medication (i.e., fluticasone or Flonase®) or nasal irrigation. Participants who have been previously using a nasal spray or nasal irrigation will be asked to discontinue use while enrolled in the study.

Patient-reported Outcome Measure

The SNOT-22 (©2006, Washington University, St. Louis, MO) will be used to capture the physical, functional, and emotional consequences of rhinosinusitis. The SNOT-22 is a validated, patient-reported outcome measure applicable to chronic sinonasal conditions.³³ The severity of 22 rhinosinusitis-related symptoms and physical signs are measured using a Likert scale as follows: 0= "No problem"; 1="Very mild problem"; 2="Mild or slight problem"; 3="Moderate problem"; 4="Severe problem"; and 5="Problem as bad as it can be". Higher total scores on the SNOT-22 suggest worse patient functioning or symptom severity (score range: 0-110). A minimally clinically improved difference (MCID) in symptoms that is perceptible and pertinent to the individual patient on the SNOT-22 has been previously described as an improvement of at least 9 points.^{33,34}

Primary Outcome Measure

Study participants will be asked to complete the SNOT-22 at baseline, two weeks, four weeks, six weeks, and eight weeks following start of medications. The SNOT-22 score will be calculated as the average per item score for each of the 22 items and the value will range between 0 and 5. For subjects who answer less than 22 items (i.e., don't completely answer the SNOT-22), the total score will be the average per item value for the items that were answered. The change in SNOT-22 scores between baseline and eight weeks will serve as the primary outcome measure in this study and will be calculated as:

Primary Outcome Measure, $\Delta\text{SNOT-22} = \text{SNOT-22}_{\text{baseline}} - \text{SNOT-22}_{\text{8-week follow-up}}$.

To assess the trajectory of change within subjects randomized to the two treatment arms the baseline, two-week, four-week, six-week, and eight-week SNOT-22 assessment will be compared.

Secondary Outcome Measure.

University of Pennsylvania Smell Identification Test (UPSIT):

The UPSIT is a test of olfactory identification and consists of four 10-page booklets, with a total of 40 items. On each page, there is a different “scratch and sniff” strip and four choice options. Subjects are asked to scratch each strip with a pencil to release the scents, detect the smell, and identify the smell from the four choice options. The UPSIT comes from a scoring rubric that identifies the normalcy benchmark based on age and gender. The UPSIT is commercially available, takes 10-15 minutes to complete, and is the gold standard test to assess smell identification. Subjects will complete the UPSIT at their baseline and final visit.

Clinical Global Impression Scale (CGI):

The overall response to treatment will be measured with a modification of the Clinical Global Impression (CGI) scale.^{32,35} Upon completion of the study, subjects will be asked to answer the following question: "Overall, how would you rate your response to treatment?" Response options are: 1 = *Very Much Improved*, 2 = *Much Improved*, 3 = *Minimally Improved*, 4 = *No Change*, 5 = *Minimally Worse*, 6 = *Much Worse*, 7 = *Very Much Worse*. In addition, subjects will be asked to rate their subjective sense of smell pre- and post-intervention.

Questionnaire for Olfactory Dysfunction (QOD):

The QOD is a validated quality of life questionnaire for patients with olfactory disorders. Subjects will complete the QOD at their baseline and final visit.

Olfactory Dysfunction Outcomes Rating (ODOR):

The ODOR is a quality of life measure capturing physical, functional, and emotional limitations specific to smell loss. It is currently undergoing validation and is designed to be more concise, readable, and comprehensive than the QOD. Subjects will complete the ODOR questionnaire at their baseline and final visit.

Physical Examination including nasal endoscopy performed for clinical purposes The physical examinations will be done as part of routine care during the patients’ scheduled clinic visit. The findings from the endoscopic examination will be collected for research purposes and will be recorded using the grading system proposed by Lund and Kennedy.³⁶

Endoscopic Findings

	None Present	Present	
1. Crusting	0	1	
2. Erythema	0	1	
3. Swelling	0	1	
4. Scar Band	0	1	
5. Purulent Drainage	0	1	
6. Thick Mucous	0	1	
	None Present	Present in middle meatus	Present outside middle meatus
7. Polyps	0	1	2

Radiologic Examination

Radiologic examination, including CT scan of the sinuses, will not be required for enrollment in the study. Enrolled subjects who receive a CT scan of the sinuses for clinical reasons during the period of this study will have the results of the radiologic examination collected for research

purposes and will be recorded according to the Lund MacKay system and possibly included in the data analysis.^{36,37}

Sinus system	Left	Right
Maxillary		
Anterior ethmoid		
Posterior ethmoid		
Sphenoid		
Frontal		
Ostiomeatal complex		

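### The placebo capsule is lactose only and is described as identical to a budesonide capsule, so the protocol does not assure blinding of the rinse

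*Combined protocol and SAP*

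**What the plan says.** The opening summary states that "the study design will be a double-blinded, randomized clinical trial". The Intervention section adds that participants and all of the study team except the biostatistician stay blinded, using numbered bottles and a restricted list.

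The four products are described separately in section III:

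- Mometasone rinse (Mometasone Nasal Irrigation): "The inert ingredients are: loxasperse powder, which increases solubility and dispersibility of mometasone and is microbiologically safe", followed by "mannitol, which is widely used in pharmaceutical products as a capsule diluent; and Xylifos™ powder, which is a proprietary powder excipient".
- Placebo rinse (Placebo Nasal Irrigation): lactose monohydrate, "supplied in clear plastic capsules, which are identical to the budesonide capsules". The section continues: "The capsules will only contain lactose as there are no other ingredients".
- Placebo spray (Placebo Nasal Spray): packaged in the same bottle as the active spray, and it "will contain the same inert ingredients found in MF nasal spray".
- Mometasone spray (Mometasone Nasal Spray): prepared by the study pharmacy.

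Under Intervention, every participant opens two capsules, mometasone or lactose according to arm, into the rinse bottle once a day for eight weeks and then irrigates with the mixture.

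**The concern.** A double-dummy design hides the arm only if each placebo passes for its active counterpart. The protocol meets that standard for the spray and states a different composition for the rinse, which is the delivery route under test.

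The two products are also tied together. A participant who works out which capsule they have also knows which spray they have, so a weak match on the capsule undoes the good match on the spray.

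What is at stake is the primary analysis. The change in SNOT-22 from baseline to week 8, the proportion reaching a 9-point improvement, and the Clinical Global Impression all rest on the participant's own rating. If participants infer their arm, expectation can enter these ratings, and the planned t-test and chi-square tests cannot separate that from a treatment effect.

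**Working it through.** The point carries no figure to reproduce, so the check is a comparison of the product descriptions.

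| | Rinse capsule | Spray |
|---|---|---|
| Active: inert ingredients | Loxasperse, mannitol, Xylifos | As listed under Placebo Nasal Spray |
| Placebo: ingredients | Lactose only | Same list as the active spray |
| Active excipients shared by the placebo | 0 of 3 | All |
| Stated match of container | Clear capsule, identical to the budesonide capsule | Same bottle as the active spray |

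1. **Composition.** None of the three excipients of the active rinse is in the placebo, and lactose is not listed for the active. This is a stated composition, not a missing detail. The protocol says of loxasperse that it aids solubility and dispersion, so by its own account this excipient is there to affect how the powder behaves in liquid.

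2. **Appearance.** The only statement of visual match is "which are identical to the budesonide capsules". Budesonide appears elsewhere in the protocol only as background, including an earlier budesonide rinse trial at the same institution. The Intervention section names this trial's capsules correctly as mometasone or lactose. The word may therefore be carried over. If mometasone was meant, the shells match, but they are clear and are emptied by the participant, so the contents are still seen.

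3. **Exposure.** The participant handles the powder, disperses it and rinses with it daily. Medications are mailed from the pharmacy to the participant, so the risk lies mainly with the participant, who is also the rater of the primary outcome.

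4. **Other safeguards.** Numbered bottles and the restricted list protect the allocation code. They do not make two different powders look, disperse or taste alike.

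5. **Corrections elsewhere.** No other section states that the placebo capsule matches the mometasone capsule in look, fill, dispersion or taste, and no check of blinding is planned.

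**The case against.** The strongest reply is that unblinding is inferred and not shown. The documents give no colour, fill, taste or solubility for either powder. Each participant receives one kind of capsule, has nothing to compare it with, and would need to know which appearance means mometasone. Everyone irrigates, everyone sprays, and everyone receives active drug by one route, which limits the pull of expectation. All of this stands. It supports saying that blinding is not assured, and nothing stronger.

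A reader might also infer that the trial fails to isolate mometasone, because the active rinse carries a vehicle that the placebo lacks. The documents do not support making that the complaint. Both arms receive mometasone. The primary objective compares irrigation with spray as delivered, and a dispersant can fairly be seen as part of the irrigation product. The Statement of the Research Problem does speak of adding mometasone to a rinse, but it goes on to set the comparison against mometasone spray combined with saline irrigation. The protocol calls the excipients inert, and nothing in it suggests that they change the SNOT-22.

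Finally, the budesonide wording is most plausibly a carry-over and is weak evidence of a blinding failure by itself. That is fair, but the sentence is the protocol's only statement of capsule match and needs to be right.

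**Conclusion.** The point holds in limited form. The protocol specifies a placebo capsule that differs in composition from the active capsule and names the wrong product as its visual match, so the stated double-blinding of a participant-reported primary outcome is not assured.

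The size of any bias cannot be derived from the documents. A count of capsules opened over eight weeks would measure opportunity, not bias. Nor would it be right to say that all participants take the unmatched placebo: only the spray arm takes the lactose capsule, and the irrigation arm takes the mometasone capsule.

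The conclusion rests on two assumptions: that the ingredient lists are complete as written, and that participants can see the contents when they open clear capsules. It does not assume that anyone has been or will be unblinded. This is a worthwhile, inexpensive improvement to make before capsules are supplied, because a mismatch cannot be repaired at analysis.

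**What to change.** In Placebo Nasal Irrigation, specify that the placebo capsule contains the same inert ingredients as the mometasone capsule, without mometasone, in the same shell. This applies the standard already set for the placebo spray. In the same sentence, correct budesonide to mometasone.

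The cost is a compounding change by the supplier of the placebo capsules. The protocol says that the pharmacy prepares the mometasone capsules and provides both kinds. It does not say who compounds the placebo capsules, so the sponsor should confirm this first.

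Asking participants at week 8 which arm they believe they were in is optional. It adds one question, but late guesses also reflect perceived benefit, so it is no substitute for matching the capsules.
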